### **Strong CYP3A Inhibitors or Inducers**

Systemic use of known strong CYP3A inhibitors (includes over-the-counter or prescription medicines, vitamins, and/or herbal supplements) is not permitted from Screening through the end of study drug administration and use of strong CYP3A inducers is not permitted from 30 days prior to study drug administration through the end of study drug administration. [Table 1](#) includes examples of commonly used strong CYP3A inhibitors and inducers. In addition, herbal therapies and other traditional medicines with unknown effects on CYP3A are not permitted from Screening through the end of study drug administration.

**Table 1. Examples of Commonly Used Strong CYP3A Inhibitors and Inducers**

Strong CYP3A Inhibitors	Strong CYP3A Inducers
Boceprevir	Avasimibe
Clarithromycin	Carbamazepine
Cobicistat	Phenytoin
Conivaptan	Rifampin (Rifampicin)
Grapefruit (fruit or juice)	Rifapentine
Indinavir	St. John's Wort
Itraconazole	
Ketoconazole	
Lopinavir/Ritonavir	
Mibepradil	
Nefazodone	
Nelfinavir	
Posaconazole	
Ritonavir	
Saquinavir	
Telaprevir	
Telithromycin	
Troleandomycin	
Voriconazole	

#### **Elective and Emergency Surgeries:**

Elective surgery will not be allowed during the study until the primary endpoint has been assessed (Week 24). If the subject undergoes elective surgery, the study drug should be interrupted 1 week prior to the planned surgery. Allow reintroduction of study drug once the physician has examined the surgical site and determined that it has healed and there is no sign of infection.

If the subject must undergo emergency surgery, the study drug should be interrupted at the time of the surgery. After emergency surgery, allow reintroduction of study drug once the physician has examined the surgical site and determined that it has healed and there is no sign of infection.

#### **5.4 Prior and Concomitant Therapy**

Any medication or vaccine (including over-the-counter or prescription medicines, vitamins, and/or herbal supplements) that the subject is receiving at the time of Screening and/or receives during the study must be recorded along with the reason for use, date(s) of administration including start and end

dates, and dosage information including dose, route, and frequency on the appropriate electronic case report form (eCRF). Also, medications taken for vitiligo since date of diagnosis (based on subject recollection and available medical records) should be entered into the appropriate eCRF inclusive of the dates of first and last dose, maximum dosage taken, and route of administration.

## 5.5 Withdrawal of Subjects and Discontinuation of Study

---

AbbVie may terminate this study prematurely, either in its entirety or at any site. The study may be discontinued or terminated in case of an unacceptable risk, any relevant toxicity, or a negative change in the risk/benefit assessment. This might include the occurrence of AEs with a character, severity, or frequency that is new in comparison to the existing risk profile. In addition, data deriving from other clinical trials or toxicological studies which negatively influence the risk/benefit assessment might cause discontinuation or termination of the study. The investigator may also stop the study at his/her site if he/she has safety concerns. If AbbVie terminates the study for safety reasons, AbbVie will promptly notify the investigator. Advance notice is not required by either party if the study is stopped due to safety concerns.

Subjects can request to be discontinued from participating in the study at any time for any reason. The investigator may discontinue any subject's participation at any time for any reason. The AbbVie Therapeutic Area Medical Director (TA MD)/Scientific Director may mandate individual subject discontinuation from study drug in case of safety concern.

Subjects must have study drug discontinued immediately if any of the following occur:

- The subject requests withdrawal from study drug or the study.
- The investigator believes it is in the best interest of the subject.
- Abnormal laboratory results or AEs that either meet the criteria for discontinuation of study drug, as stated in Section 6.2, or rule out safe continuation of the study drug, as determined by the investigator or the AbbVie TA MD.
- Serious infections (e.g., sepsis) which cannot be adequately controlled by anti-infective treatment or would put the subject at risk with continuation of the study drug.
- Confirmed diagnosis of DVT, pulmonary embolus or non-cardiac, non-neurologic arterial thrombosis.
- Subject is non-compliant with TB prophylaxis (if applicable) or develops active TB at any time during the study.
- Subject develops a malignancy, except for localized NMSC or carcinoma in-situ of the cervix.
- Subject develops a GI perforation (defined as acute, spontaneous perforation of the GI tract that requires inpatient medical care or urgent surgical intervention other than appendicitis or mechanical injury). See also Section 6.2 Toxicity Management.
- The subject becomes pregnant or plans to become pregnant while on study drug.
- Eligibility criteria violation was noted after the subject started study drug, when continuation of the study drug would place the subject at risk. Note: intentional/prospective deviations from the protocol are NOT allowed, see Section 5.9 Protocol Deviations.

- Introduction of prohibited medications or dosages when continuation of the study drug would place the subject at risk.
- Subject is significantly non-compliant with study procedures.
- Worsening vitiligo as defined by an increase of 25% or higher in T-VASI from Baseline beginning at Week 8.

Additional requirements related to abnormal laboratory values and selected AESIs are located in Section [6.2](#).

During the COVID-19 pandemic, it has been necessary to employ mitigation strategies to enable the investigator to ensure subject safety and continuity of care. The investigator should contact the sponsor medical contact before discontinuing a subject from the study for a reason other than "planned per protocol," to ensure all acceptable mitigation steps have been explored.

## 5.6 Follow-Up After Subject Discontinuation

---

If a subject prematurely discontinues study drug, the procedures outlined for the Premature Discontinuation (PD) Visit should be completed as soon as possible, preferably within 2 weeks of study drug discontinuation, and preferably prior to initiation of another therapy. In addition, a 30-day Follow-up Visit or phone call should occur to determine the status of any ongoing AEs/SAEs or the occurrence of any new AEs/SAEs.

For subjects to be considered lost to follow-up, reasonable attempts must be made to obtain information on the subject's final status. At a minimum, 2 telephone calls must be made and 1 certified letter must be sent and documented in the subject's source documentation.

If a subject withdraws from study follow up or withdraws permission for the collection of their personal data, the study staff may still use available public records to obtain information about survival status only, as appropriate per local regulations.

In the event a subject withdraws consent from the clinical study, biomarker research will continue unless the subject explicitly requests analysis to be stopped. When AbbVie is informed the subject has withdrawn and no longer wishes biomarker research to continue, samples will not be analyzed, no new biomarker analysis data will be collected for the withdrawn subject or added to the existing data or database(s), and the samples will be destroyed. A subject may withdraw consent for optional biomarker research at any time and remain in the clinical study. Data generated from clinical study and/or optional biomarker research, before subject withdrawal of consent, will remain part of the study results.

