#### Primary

The primary objective of this study is to evaluate the safety and efficacy of upadacitinib for the treatment of adult subjects with NSV.

The primary efficacy objective is based on the percent change from Baseline in Facial Vitiligo Area Scoring Index (F-VASI) at Week 24 with upadacitinib treatment compared to placebo in the Intent-to-Treat (ITT) Population, which consists of all randomized subjects (Section 7.2).

The hypothesis corresponding to the primary endpoint (Section 3.2) is:

- Percent change from Baseline in F-VASI with upadacitinib is greater than that with placebo at Week 24.

The estimand corresponding to the primary endpoint is defined as:

- Difference in the percent change from Baseline in F-VASI at Week 24, regardless of treatment discontinuation, between each of the upadacitinib dose groups compared with placebo in the ITT Population.

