## 7.3 Handling Potential Intercurrent Events for the Primary Endpoint

---

The primary endpoint (Section 3.2) will be analyzed in the ITT Population and no intercurrent events will be considered. All data collected, regardless of premature discontinuation of study drug, will be used in the analysis.

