2.0 Study Design and Objectives

2.1 Objectives, Hypotheses and Estimands

The primary objective of this study is to evaluate the safety and efficacy of upadacitinib for the treatment of adult subjects with NSV. The primary efficacy objective is based on the percent change from Baseline in Facial Vitiligo Area Scoring Index (F-VASI) at Week 24 with upadacitinib treatment compared to placebo in the Intent-to-Treat (ITT) Population, which consists of all randomized subjects.

The hypothesis corresponding to the primary endpoint is:

Percent change from Baseline in F-VASI with upadacitinib is greater than that with placebo at Week 24.

The estimand corresponding to the primary endpoint is defined as:

Difference in the percent change from Baseline in F-VASi at Week 24, regardless of treatment discontinuation, between each of the upadacitinib dose groups compared with placebo in the adult subjects with NSV.

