8.0 Handling of Potential Intercurrent Events for the Primary Endpoint

The primary efficacy endpoint of percent change in F-VASI at Week 24 (defined in Section 3.1) will be analyzed based on the ITT_1 Populations. For treatment policy strategy, the occurrence of the intercurrent event (treatment discontinuation) is considered as irrelevant in defining the treatment effect of interest. Under this strategy, the value for the variable of interest is used regardless of whether or not the intercurrent event occurs.

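### Week 24 F-VASI after study drug is stopped: the protocol text does not state whether it is collected, and both planned analyses of the primary endpoint assume missing at random

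*Protocol*

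**What the plan says.** **The target.** Protocol 3.1 defines the estimand as "Difference in the percent change from Baseline in F-VASI at Week 24, regardless of treatment discontinuation". SAP 2.1 repeats it ("regardless of treatment discontinuation, between each of the upadacitinib dose groups compared with placebo in the adult subjects with NSV"). SAP 8.0 and Table 2 name the treatment-policy strategy for treatment discontinuation, under which "the value for the variable of interest is used regardless of whether or not the intercurrent event occurs".

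**Data use.** Protocol 7.3: "All data collected, regardless of premature discontinuation of study drug, will be used in the analysis". This governs the use of data that exist. It does not say which data are to be obtained.

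**Follow-up after stopping.** Protocol 5.6: "If a subject prematurely discontinues study drug, the procedures outlined for the Premature Discontinuation (PD) Visit should be completed as soon as possible", with the timing "preferably within 2 weeks of study drug discontinuation, and preferably prior to initiation of another therapy". The only other contact named for a subject who stops drug is a visit or call at 30 days about adverse events.

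**Reasons for stopping.** The list in Protocol 5.5 includes "The subject requests withdrawal from study drug or the study", which treats leaving drug and leaving the study as different things, and "Worsening vitiligo as defined by an increase of 25% or higher in T-VASI from Baseline beginning at Week 8", which depends on outcome.

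**Analysis.** SAP 9.2 specifies an MMRM and states that it assumes missing at random (MAR). SAP 9.3.3 lists one sensitivity analysis: multiple imputation with 30 datasets, using treatment, the stratification factors, Baseline and the Period 1 visit values. SAP Appendix E, section 2.2, says that the MI procedure assumes MAR. Protocol 7.4 left room for further sensitivity analyses; SAP 9.3.3 adds none.

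**The concern.** A treatment-policy estimand asks what happened by Week 24 to everyone randomized, including those who stopped. If stoppers have no Week 24 F-VASI, the MMRM predicts it from their own earlier visits and from subjects in the same arm who were observed at Week 24, most of them presumably still on drug. That prediction matches the estimand only if stopping does not change the later course.

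The imputation analysis conditions on essentially the same information. It has no term for being off drug, no delta and no reference arm, so close agreement between the two would be expected and would not be evidence of robustness. A PD Visit held soon after the last dose, and preferably before other therapy, says little about the later off-drug course.

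What is at stake is the size of the effect. SAP 9.3.2 feeds the primary-analysis estimates into MCP-Mod and sets the minimum effective dose (MED) at a 40-point difference from placebo, so an error of a few points carries through to the dose-response output.

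**Working it through.** **Inputs from the documents** (Protocol 7.8, SAP 2.4): difference 40 points, SD 54.8, 40 subjects per comparison group, two-sided alpha 0.1, stated power above 90%.

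**Reproducing the plan's figure.** Power is 94.7% by the normal approximation and 94.4% by the t-test, for one dose against placebo. The stated figure holds and is not in dispute.

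**Planning precision.**
- SE = 54.8 × √(2/40) = 12.25 points.
- Smallest significant difference = t(0.95, 78 df) × SE = 1.6646 × 12.25 = 20.4 points.

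**Assumed quantities** (none is in the documents):
- q = share of an active arm that stops and has no Week 24 value
- L = share of the 40-point benefit those subjects have lost by Week 24
- p = share of placebo that stops and has no Week 24 value
- w = points by which placebo stoppers end worse than the MAR prediction (negative if later therapy helps them)

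The MAR difference is 40. The treatment-policy difference is 40 − 40qL + pw. Overstatement is therefore 40qL − pw.

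| q | L | p | w | Overstatement (points) | In planning SEs |
|---|---|---|---|---|---|
| 10% | 0.5 | any | 0 | 2 | 0.16 |
| 10% | 1 | any | 0 | 4 | 0.33 |
| 20% | 0.5 | any | 0 | 4 | 0.33 |
| 20% | 1 | any | 0 | 8 | 0.65 |
| any | 0 | any | 0 | 0 | 0 |
| 10% | 0.5 | 20% | 20 | −2 | −0.16 |
| 10% | 0 | 20% | 20 | −4 | −0.33 |

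**Tipping point.** With the SE held at 12.25, active-arm stoppers must be (observed difference − 20.4)/q points worse than imputed before significance is lost.
- Observed 40: 19.6/0.10 = 196 points, or 19.6/0.20 = 98 points.
- Observed 25: 4.6/0.10 = 46 points, or 4.6/0.20 = 23 points.

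**Effect on the MED, one illustration.** Take the Emax shape in SAP Table 3 with ED50 fixed at its initial value of 2.41, and assume a MAR difference of 48 points at 22 mg.
- Emax = 48 × (2.41 + 22)/22 = 53.26.
- MED for 40 points = 40 × 2.41/(53.26 − 40) = 7.3 mg.
- If 10% of every active arm stop and lose half the benefit, Emax becomes 0.95 × 53.26 = 50.60 and the MED 96.4/10.60 = 9.1 mg.
- If they lose all of it, Emax becomes 0.90 × 53.26 = 47.93 and the MED 96.4/7.93 = 12.2 mg.

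The second case is an error of 4.8 points at 22 mg, and it moves the computed MED from below the 11 mg arm to above it. Other shapes, fitted ED50 values and AIC weights would give other numbers.

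**The case against.** **Continued follow-up may well be intended.** Protocol 5.5 separates stopping drug from leaving the study. SAP 5.0 counts completion of Period 1 apart from completion of study drug. Protocol 5.6 treats withdrawal from follow-up as its own event, and nothing says that visits end when drug stops. Against this, SAP Appendix E, section 2.1, gives study-drug discontinuation as an example of a reason for missing data. The operations manual (Appendix F) describes the activities and was not available. The F-VASI row of Appendix D is also broken in the extracted text, with 17 ticks for 14 visit columns, so it cannot show whether F-VASI is done at the 30-day visit. All of this stands. A reader might infer that F-VASI is not collected after the PD Visit; the documents do not support that.

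**The worsening rule is less damaging than it looks.** A reader might infer that it makes the missing data non-ignorable. F-VASI and T-VASI share one row of the schedule, so a visit that triggers the rule should also supply an F-VASI value, and both models condition on observed F-VASI. Only dependence on T-VASI beyond the F-VASI history is left out.

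**The magnitudes are assumed.** This is right. A reader might infer that the trial overstates the effect by 2 to 8 points. The documents give neither stopping rates nor the off-drug course of upadacitinib. The relapse figure in Protocol 2.2 concerns phototherapy.

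**This is Phase 2, at alpha 0.1 without multiplicity control, and NRI-MI already gives a non-MAR view.** NRI-MI helps only for the binary endpoints, and it uses MI wherever data are judged missing at random. The phase lowers the stakes for significance, but a dose-ranging trial depends on effect size.

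**Conclusion.** The concern holds in limited form. The plan states a treatment-policy estimand, does not state in the supplied text whether the Week 24 values it needs from stoppers are collected, and contains no analysis of the primary endpoint that departs from MAR. The analysis part stands whatever the operations manual says, because some stoppers will probably not return.

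Direction and size are unknown. The range of 2 to 8 points rests on 10 to 20% stopping with no Week 24 value, loss of half to all of a 40-point benefit, and placebo stoppers who follow the MAR prediction. Other plausible inputs give zero or an understatement. A reader might also infer that the significance of the primary result is in doubt. At the planned 40-point effect it is not: stoppers would have to be 98 to 196 points worse than imputed. At an observed difference nearer 25 points the margin is much thinner, at 23 to 46 points. This should be fixed; confidence is medium, because the operations manual was not seen.

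**What to change.** 1. **SAP 9.3.3: add one non-MAR analysis of the primary endpoint.** Reuse the 30 imputed datasets already planned. Add a delta to the imputed Week 24 percent change of subjects who stopped drug. Vary it separately in the active and placebo arms, in both directions, and report where the conclusion changes. A reference-based imputation would also serve.

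2. **Protocol 5.6 and Appendix D: state the collection rule.** Subjects who stop study drug without withdrawing consent keep the F-VASI assessments already scheduled through Week 24, or at minimum the Week 24 one. If the operations manual already says this, cite it in 5.6.

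The second step does not replace the first. Suppose 20% of an active arm stop and half return. If the returners have kept all their benefit and the others have lost all of it, the true difference is 40 − 0.10 × 40 = 36. The MAR estimate is still 40, so the error stays at 4 points. Collection reduces the error reliably only if returners resemble those who do not return.

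**Cost.** A short amendment and a little programming on existing datasets. At an assumed 10 to 20% stopping in all arms, the Week 24-only option is at most 0.10 × 160 = 16 to 0.20 × 160 = 32 assessments, with no new procedure. The estimand itself need not change.

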## 5.7 Study Drug

---

Study drug will be taken orally QD, beginning on Day 1 (Baseline), and should be taken at approximately the same time each day, with or without food. Subjects will be instructed to return all drug containers (even if empty) to the study site personnel at each study visit; study site personnel will document compliance.

AbbVie will not supply any vitiligo disease-related concomitant medication therapy taken during the course of the study. AbbVie will supply upadacitinib and matching upadacitinib placebo.

Study drug will be packaged in quantities sufficient to accommodate the study design.

Each kit will be labeled per local requirements and this label must remain affixed to the kit. Upon receipt, study drug should be stored as specified on the label and kept in a secure location. Each kit will contain a unique kit number. This kit number is assigned to a subject via interactive response technology (IRT) and encodes the appropriate study drug to be dispensed at the subject's corresponding study visit. All blank spaces on the label will be completed by the site staff prior to dispensing to subjects. Study drug will only be used for the conduct of the study.

The individual study drug information is presented in [Table 2](#).

**Table 2. Description of Study Drug**

Investigational Product	Mode of Administration	Dosage Form	Strength	Blinded or Open Label	Frequency	Manufacturer
Upadacitinib (ABT-494)	Oral	Extended-release, film-coated tablets	6 mg, 11 mg, or 22 mg	Blinded	QD	AbbVie
Placebo for upadacitinib (ABT-494)	Oral	Film-coated tablets	Not applicable	Blinded	QD	AbbVie

During the COVID-19 pandemic, study drug shipment can be made from the study site to the subject if allowed by local regulations. Refer to the operations manual for details on direct-to-patient shipment of study drug.

## 5.8 Randomization/Drug Assignment

All subjects will be assigned a unique identification number by the IRT at the Screening Visit. For subjects who rescreen, the screening number assigned by the IRT at the initial screening visit should be used. The IRT will assign a randomization number that will encode the subject's treatment group assignment according to the randomization schedule. Subjects who meet eligibility criteria at Baseline will be randomized in a 2:2:2:1:1 ratio to one of the five treatment groups:

- Group 1: upadacitinib 22 mg QD (N = 40) (Period 1) → upadacitinib 22 mg QD (Period 2)
- Group 2: upadacitinib 11 mg QD (N = 40) (Period 1) → upadacitinib 11mg QD (Period 2)
- Group 3: upadacitinib 6 mg QD (N = 40) (Period 1) → upadacitinib 6 mg QD (Period 2)
- Group 4: placebo (N = 20) (Period 1) → upadacitinib 22 mg QD (Period 2)
- Group 5: placebo (N = 20) (Period 1) → upadacitinib 11 mg QD (Period 2)

Randomization will be stratified by the age group ( $\leq 50$  and  $> 50$ ), Baseline disease severity (T-VASI  $< 15$  and  $\geq 15$ ), and status of active vitiligo (Yes/No) defined as follows:

- Active: Showing new lesions or progression (enlargement) of existing lesions within the last 6 months and/or presenting clinical subtypes indicative of progressing vitiligo (i.e., confetti-like depigmentation, trichrome pattern, or Koebner phenomenon).

At Week 24, subjects who were randomized to placebo at Baseline will be switched to either 22 mg (Group 4) or 11 mg (Group 5) upadacitinib in a blinded fashion per pre-specified randomization assignments.

All AbbVie personnel with direct oversight of the conduct and management of the trial (with the exception of AbbVie Drug Supply Management Team) will remain blinded to each subject's treatment until the Week 24 primary analysis for the study, while the investigator, study site personnel, and the subject will remain blinded to each subject's treatment throughout the study. To maintain the blind, the upadacitinib tablets and placebo tablets provided for the study will be identical in appearance. The IRT will provide access to unblinded subject treatment information in the case of a medical emergency.

In the event of a medical emergency that requires unblinding of the study drug assignment, the investigator is requested to contact the AbbVie TA MD prior to breaking the blind. However, if an urgent therapeutic intervention is necessary which warrants breaking the blind prior to contacting the AbbVie TA MD, the investigator can directly access the IRT system to break the blind without AbbVie notification or agreement. Unblinding is available in the IRT system via the Unblind Subject transaction, which is available only to the investigator. If the IRT system is unavailable, unblinding may occur by contacting the technical support of the IRT vendor via either phone (preferred) or email ([[contact]](mailto:[contact])). For country-specific phone numbers, please see the following website: <http://www.endpointclinical.com/helpdesk/>.

In the event that the blind is broken before notification to the AbbVie TA MD, we request that the AbbVie TA MD be notified within 24 hours of the blind being broken. The date and reason that the blind was broken must be conveyed to AbbVie and recorded on appropriate eCRF.

